7.6 Other Safety Data

7.6.1 Targeted Neurological Assessment

The targeted neurological examination and neurological consult evaluation results with unexplained abnormal neurological findings will be summarized at screening and at each visit and by treatment group as listed in Appendix 16.6. The number and percentage of subjects with targeted neurological examination in each of the neurological domains (vision, motor, tactile sensation, coordination/cerebellar function, speech, verbal comprehension, and cognition/behavior) will be summarized by the result category (abnormal, normal, not done) at each visit and by treatment group as listed in Appendix 16.6. The number and percentage of subjects who were referred for a neurological consultation and the results (no PML, PML, no clinically significant finding, other clinically significant finding, not done, other) will also be summarized by treatment group as listed in Appendix 16.6. The neurological evaluation and consultation results will be listed for the Safety Set.

7.6.2 Immunogenicity

Presence of ADAs will be listed and summarized by visit for each treatment group as listed in Appendix 16.6.

Anti-drug antibodies will be classified into pre-existing, treatment-induced responses, and treatment-boosted responses. Pre-existing is defined as a signal detected prior to treatment. Treatment-induced responses are defined as a negative pretreatment sample with at least 1 positive sample at a subsequent time point. Treatment-boosted responses are defined as positive pretreatment samples that are boosted to a higher level following drug administration. Those categories will be listed and summarized by treatment group as listed in Appendix 16.6.

Neutralizing antibodies will be tested on ADA-positive subjects, and samples will be defined as NAb-positive or -negative. Presence of NAbs will be listed and summarized for all ADA-positive subjects by visit for each treatment group as listed in Appendix 16.6.

Anti-drug antibody prevalence will also be calculated and summarized by treatment group as listed in Appendix 16.6. Antidrug antibody prevalence is the proportion of study population having drug-reactive antibodies (ADA) at any time point (including pre-existing antibodies) during the study.

Anti-drug antibody incidence will be calculated and summarized by treatment group as listed in Appendix 16.6. Anti-drug antibody incidence is the proportion of study population found to have developed ADA or boosted their ADA (including pre-existing ADA) at any point during the study period.

Listings of positive immunogenicity results and individual subject immunogenicity data will be presented.

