**Figure 4 Potential Immunogenicity of Therapeutic Monoclonal Antibodies**

Ontamalimab is a fully human antibody of the immunoglobulin G2 subclass. In Phase 1 and Phase 2 clinical trials of ontamalimab, in which over 700 subjects were treated for up to 3 years, there has been no case of anaphylaxis. There have been 2 reported cases of drug hypersensitivity: serum sickness attributed to concomitant administration of penicillin; and a reaction characterized by dyspnea, facial erythema, and chest pain with onset 2 days after administration of the fifth dose of ontamalimab. The latter event mimicked a reaction that the subject had previously experienced after 4 doses of infliximab. In addition, low titer activity has been observed in ADA assays, including pretreatment samples and placebo-treated subjects, and no subject has had a 2-fold or greater increase in ADA titer. Analysis of PK and clinical

parameters has shown no difference between subjects whose ADA assays results are positive as compared with those whose are negative.

Nonetheless the possibility of a hypersensitivity reaction occurring after drug exposure cannot be fully ruled out. The reactions of concern are Type I (anaphylaxis) and Type III (immune complex) reactions. The clinical presentation of anaphylactic reactions is described in [Table 6](#).

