7. SAFETY ANALYSIS

The safety analyses will be performed using the Safety Set. Safety variables include adverse events (AEs), clinical laboratory variables, vital signs, electrocardiogram (ECG) variables, anti-drug antibody (ADA) and neutralizing antibody (NAb) variables, and neurological variables. For each safety variable, the last value collected prior to the first dose of double-blind IP in induction study (SHP647-301 or SHP647-302) will be used as baseline for all analyses of that safety variable. A final on-treatment assessment will be defined as the last valid assessment obtained after MNT baseline and through the end of treatment visit.

Safety outputs will be presented by treatment group listed in Appendix 16.6. The primary set will present data by SHP647-303 treatment, regardless of the treatment in the induction study. The secondary set will present data by both the induction study treatment and the SHP647-303 study treatment.

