7.2 Clinical Laboratory Data

Descriptive statistics for clinical laboratory values (in conventional units) and changes from induction study (SHP647-301 or SHP647-302) baseline at each assessment time point for quantitative variables will be presented by treatment group as listed in Appendix 16.6 for the following clinical laboratory variables. The number and percentage of subjects for qualitative variables in urinalysis will be presented by treatment group as listed in Appendix 16.6 in the Safety Set.

Serum chemistry

- alkaline phosphatase
- aspartate aminotransferase (AST)
- alanine aminotransferase (ALT)
- total bilirubin
- total protein
- albumin
- glucose
- blood urea nitrogen
- creatinine
- sodium
- potassium
- chloride
- calcium
- carbon dioxide

Hematology

- hemoglobin
- hematocrit
- mean corpuscular hemoglobin
- mean corpuscular hemoglobin concentration
- mean corpuscular volume
- erythrocyte (red blood cell) count
- leukocyte (white blood cell) count
- neutrophils
- lymphocytes
- monocytes
- eosinophils
- basophils
- platelet count

Urinalysis

- glucose
- protein
- specific gravity
- pH
- nitrite
- bilirubin
- ketones
- hemoglobin
- urobilinogen
- leukocyte esterase

Clinical laboratory test values are potentially clinically important (PCI) if they meet either the low or high PCI criteria listed in Table 3. The number and percentage of subjects with post-MNT baseline (value collected after the first exposure to IP in the SHP647-303 study) PCI values will be tabulated by treatment group as listed in Appendix 16.6. The percentages will be calculated relative to the number of subjects with at least 1 post-MNT baseline assessment. The numerator is the total number of subjects with at least 1 post-MNT baseline PCI value. A supportive listing of subjects with post-MNT baseline PCI values will be provided including the subject number, site, induction study (SHP647-301 or SHP647-302) baseline, MNT baseline, and post-MNT baseline values.

Figures will be presented for hematology and chemistry to show the changes in laboratory parameters over time. Data will be presented as box-and-whisker plots by treatment group as listed in Appendix 16.6 at each visit, with 1 laboratory parameter per page.

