16.6 Treatment Groups

Data will be presented by treatment group into 3 pages as follows:

Page 1 (SHP647-301 or SHP647-302 Study Treatment/SHP647-303 Study Treatment)

- Ontamalimab 25 mg/Placebo
- Ontamalimab 25 mg/Ontamalimab 25 mg
- Ontamalimab 75 mg/Placebo
- Ontamalimab 75 mg/Ontamalimab 75 mg

Page 2 (SHP647-301 or SHP647-302 Study Treatment/SHP647-303 Study Treatment)

- Placebo/Placebo
- Placebo/Ontamalimab 25 mg
- Placebo/Ontamalimab 75 mg

Page 3 (SHP647-303 Study Treatment)

- Placebo
- Ontamalimab 25 mg
- Ontamalimab 75 mg
- Ontamalimab All Doses
- Total (for disposition, demographics, and baseline characteristics tables)

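### SAP 7.6.2 leaves *pretreatment* undated, so under the SAP 7 baseline rule ADA carried in from induction counts as treatment-induced in the primary maintenance columns; a maintenance-emergent class would be a cheap improvement

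*SAP*

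**What the plan says.** SAP 7 names ADA and neutralizing antibodies among the safety variables. For each such variable, "the last value collected prior to the first dose of double-blind IP in induction study (SHP647-301 or SHP647-302) will be used as baseline", and this holds for all analyses of the variable. On display it states: "The primary set will present data by SHP647-303 treatment, regardless of the treatment in the induction study". It then adds: "The secondary set will present data by both the induction study treatment and the SHP647-303 study treatment".

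SAP 16.6 sets out the columns. Page 3 groups by SHP647-303 treatment only, so its Placebo column combines 25 mg/placebo, 75 mg/placebo and placebo/placebo. Pages 1 and 2 show the induction/maintenance sequences separately.

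SAP 7.6.2 has three ADA classes: pre-existing, treatment-induced and treatment-boosted. All three are set by status before treatment and by later samples. The middle one reads: "Treatment-induced responses are defined as a negative pretreatment sample with at least 1 positive sample at a subsequent time point". Incidence is the proportion of the study population "found to have developed ADA or boosted their ADA (including pre-existing ADA) at any point during the study period". ADA presence by visit, listings of positive results and individual listings are also planned. The section does not say which treatment pretreatment precedes. It does not mention the maintenance (MNT) baseline, which SAP 5.2 defines as the induction Week 12 value. SAP Table 7 maps ADA samples to Weeks 12, 24 and 36, starting at Day 2.

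**The concern.** Take a subject who was ADA-negative before induction, turned positive on induction ontamalimab, was re-randomised to placebo and is positive again in SHP647-303. Under the SAP 7 baseline rule this subject is treatment-induced, and on the primary display is counted under Placebo. A reader of that page would naturally take the Placebo rate as a background against which to judge maintenance ontamalimab. It is not a drug-free background, because most of those subjects had the drug in the preceding 12 weeks.

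The sequence pages separate subjects by induction exposure, but not by when ADA first appeared. Within the 25/25 and 75/75 columns, ADA already present at entry and ADA new in maintenance fall into one class and one incidence figure.

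At stake is the reading of a named potential risk: SAP 7.1.1 lists immunogenicity. No efficacy conclusion or error rate is affected.

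**Working it through.** **1. Which baseline applies.** SAP 7.6.2 leaves the term undefined, so there are two readings.

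- *Pre-induction*, from the SAP 7 rule, to which 7.6.2 states no exception. ADA acquired in induction and still present is treatment-induced.
- *Pre-SHP647-303*. The same ADA becomes pre-existing and is merged with ADA present before any ontamalimab. New ADA is then separated, but natural and induction-acquired ADA are not.

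The first follows from the written rule. Neither reading gives three distinct groups (natural, induction-acquired, maintenance-emergent). One gap remains even on the first: for ADA that resolved before the first SHP647-303 sample, the SAP does not say whether the induction Week 12 sample counts as a later time point. The figures below therefore cover only ADA detected again in SHP647-303.

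**2. Exposure mix of the primary columns.** Inputs are from Protocol 9.6 and 3.1. Planned entry is 296 (25 mg induction), 296 (75 mg induction) and 104 (placebo induction), which adds to the stated 696. Allocation is 1:1 same dose versus placebo for induction-ontamalimab responders, and 2:2:1 (25 mg, 75 mg, placebo) for induction-placebo responders.

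- Placebo column: 148 + 148 + 104/5 = 316.8; with induction ontamalimab, 296/316.8 = 93.4%.
- Each dose column: 148 + 104 × 2/5 = 189.6; with induction ontamalimab, 148/189.6 = 78.1%.

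**3. Range for the enrolled 366.** Their split by induction arm is not given. Let p be the fraction from placebo induction and a = 1 − p, with the two induction doses equal.

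- Placebo-column share = (a/2) / (a/2 + p/5)
- Dose-column share = (a/4) / (a/4 + 2p/5)

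| p | Placebo column | Each dose column |
|---|---|---|
| 0.10 | 95.7% | 84.9% |
| 0.149 (104/696, planned) | 93.4% | 78.1% |
| 0.20 | 90.9% | 71.4% |
| 0.25 | 88.2% | 65.2% |

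**4. Points added to the treatment-induced rate.** Let q be the percentage of induction-treated subjects whose induction-acquired ADA is detected in SHP647-303, taken as equal across arms. Points added = share × q. The values of q are assumptions; the documents give none.

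| q | Placebo (planned mix) | Each dose (planned mix) | 25/25 and 75/75 |
|---|---|---|---|
| 1% | 0.93 | 0.78 | 1.00 |
| 5% | 4.67 | 3.90 | 5.00 |
| 10% | 9.34 | 7.81 | 10.00 |

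Over p = 0.10 to 0.25, each 1% adds 0.96 to 0.88 points (Placebo) and 0.85 to 0.65 points (each dose). If the 366 follow the planned mix, the Placebo column has 366 × 316.8/696 = 166.6 subjects, of whom 366 × 296/696 = 155.7 had induction ontamalimab. The carried-in counts are then about 1.6, 7.8 and 15.6 subjects.

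**5. Effect on a Page 3 comparison.** At the planned mix, carry-in shifts dose minus placebo by 0.78 − 0.93 = −0.15 points per 1% of q. At q = 10% the shift is 7.81 − 9.34 = −1.53 points. Under these assumptions the distortion of the levels is larger than that of the difference.

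**The case against.** The strongest reply is that the plan already offers a fair contrast. Page 1 sets 25/placebo beside 25/25 and 75/placebo beside 75/75. Each pair was randomised 1:1 after the same induction dose, so carried-in ADA is balanced in expectation and the difference shows the net effect of continuing rather than stopping ontamalimab. By-visit summaries, individual listings and a placebo/placebo column on Page 2 (about 104/5 = 20.8 subjects as planned) add to this. That stands. A reader might infer that maintenance immunogenicity cannot be seen at all; the documents do not support so strong a reading. What the pairs do not do is date conversion within a column or give a maintenance incidence.

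A pre-induction reference is also defensible. Treatment-induced is an accurate label for ADA induced by induction ontamalimab, and laboratory, vital-sign and ECG changes use the same baseline. This is a reason to keep the cumulative class, not to leave it as the only one.

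The wording is open: both pretreatment and the study period in the incidence definition could be read as SHP647-303 only. That is fair, and it is why the point is conditional on the SAP 7 rule.

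A reader might also infer from SAP 7.2 that laboratory values get a maintenance-only treatment denied to ADA. That does not hold up. Potentially clinically important laboratory counts use post-entry values but do not condition on status at entry, and the ADA visit windows are post-entry too.

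Finally, parts of the SAP are redacted, and SAP 1 places table and listing specifications in a separate document. A suitable flag may exist there, so the claim is limited to the visible text.

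**Conclusion.** The point holds as a cheap improvement, not as an error that threatens a conclusion. With the SAP 7 baseline applied as written, the primary Page 3 columns count carried-in ADA as treatment-induced. About 93% of planned Placebo subjects (88% to 96% over the range examined) and about 78% in each dose column (65% to 85%) were at risk of contributing it.

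A reader might infer from the illustrative table that the Placebo rate is inflated by several points. The documents do not support any such figure, because they give no ADA rates for this study. The evidence on consequences is reassuring: for the Phase 1 and 2 trials, Protocol 8.1.3.1 reports that "no subject has had a 2-fold or greater increase in ADA titer" and that PK and clinical parameters did not differ by ADA status. Hypersensitivity is adjudicated and tabulated separately (SAP 7.1.1.1), the ADA tables are descriptive, and ontamalimab will not be further developed.

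The conclusion rests on the pre-induction reading of pretreatment, on persistence of ADA to at least one SHP647-303 sample, and on the planned entry numbers or the stated range for p.

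**What to change.** In SAP 7.6.2:

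- State that pretreatment means before the first induction dose for the cumulative classification, and keep that classification.
- Add an SHP647-303-emergent class: ADA-negative at MNT baseline and positive later, or boosted over the MNT-baseline titer.
- Show two further categories separately: positive at MNT baseline and induction-acquired; and MNT baseline missing.
- Base the SHP647-303 ADA incidence on the emergent class, for Pages 1 to 3 of SAP 16.6.

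The cost is SAP wording, one derived flag and a small table addition, with no new samples. The downside is reliance on induction Week 12 ADA results. Protocol Table 1 footnote a and Protocol 7.2.1 carry the induction Week 12 assessments over as this study's baseline, but the induction schedules are not in these documents, so availability for ADA is an assumption. If many results are missing, the missing category will show it.

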7.6.3 Contraception Check

Contraception check should be performed for female subjects of childbearing potential and male subjects who are with a partner of childbearing potential. Contraception check results will be listed for the Safety Set.

7.6.4 Physical Examination

Complete and targeted physical examinations will be performed at the time points specified in Appendix 16.1. Physical examination results will be listed for the Safety Set.

8. [REDACTED]

8.1 [REDACTED]

[REDACTED]

8.2 [REDACTED]

[REDACTED]

8.3 [REDACTED]

[REDACTED]

8.4 [REDACTED]

[REDACTED]

9. [REDACTED]

[REDACTED]

[REDACTED]

- [REDACTED]
- [REDACTED]

[REDACTED]

[REDACTED]

[REDACTED]

10. OTHER ANALYSES

10.1 Coronavirus Pandemic

The coronavirus (COVID-19) pandemic of 2019-20 particularly poses risks to the safety of subjects enrolled in clinical trials, and the availability and interpretability of data from those trials. COVID-19 impacts on individual subjects collected on COVID-19 CRF pages will be listed for the Randomized set. Protocol deviations related to COVID-19

will be listed for the Randomized Set. The study disruptions related to COVID-19 will be listed for the Safety Set.

11. INTERIM ANALYSIS/DATA MONITORING (REVIEW) COMMITTEE

A data monitoring committee (DMC) was set up to review the safety during the course of the study. The DMC will not review efficacy data until the time of unblinding. No interim analyses are planned for this study.

12. DATA HANDLING CONVENTIONS

12.1 General Data Reporting Conventions

Continuous variables will be summarized using the following descriptive statistics: n, mean, median, standard deviation, minimum, and maximum. For the summary statistics of all numerical variables, unless otherwise specified, minimum and maximum will be displayed to the same level of precision as reported. Mean and median will be displayed to 1 level of precision greater than the data collected. Standard deviation will be displayed to 2 levels of precision greater than the data collected.

Categorical and count variables will be summarized by the number of subjects (n) and the percentage of subjects in each category. Percentages will be presented to 1 decimal place. When count data are presented, the percentage will be suppressed when the count is zero. A row denoted “Missing” will be included in count tabulations only if there are missing values. The denominator for all percentages will be the number of subjects in that treatment within the population of interest, unless otherwise specified.

P-values will generally be presented to 3 decimal places; values less than 0.001 will be presented as <0.001.

‘ONTA’ is the acronym of ontamalimab which will be used in output treatment presentation.

12.2 Definition of Treatment Failure

Treatment failure is declared for those randomized into the SHP647-303 study prior to Protocol Amendment 2 when an endoscopic subscore that has increased by at least 1 point over baseline in this maintenance study or a value of at least 2 and an increase in clinical subscore (SF plus RB score) of at least 2 points.

Treatment failure is declared for those randomized into the SHP647-303 study under Protocol Amendment 2 when the 3 following conditions are met:

- E-diary documented sustained* symptomatic worsening that includes RB
- No other etiology (ie, infection) can be identified
- Endoscopy confirms disease activity.

*Sustained: for at least 1 week if the RB score has increased by ≥ 2 points, or at least 2 weeks if the RB score has increased by < 2 points.

If treatment failure is not confirmed, subjects may continue with their next scheduled visit.

12.3 Definition of Visit Windows

Assessments will be assigned to visits based upon the date the assessment took place regardless of the completed CRF page. Assessments will be mapped to visits as outlined in [Table 6](#) to Table 9.

Should there be more than 1 assessment mapped into a given study visit with nonmissing results, the assessment closest to the planned visit will be used for analysis (referred to as analysis visit); in case of ties between observations, the later assessment will be used.

Study day will be calculated as follows:

- If the assessment date is on or after the date of first dose of IP:

$$\text{Study day} = \text{assessment date} - \text{first dosing date} + 1$$

- If the assessment date is before the date of first dose of IP:

$$\text{Study day} = \text{assessment date} - \text{first dosing date}$$

Table 6: Visit Windows (Study Day Based) – PRO, Partial Mayo, Vital Sign, Weight, and Endoscopy Assessments

Visit	Planned Study Day	Start Day of Window	End Day of Window
Week 4	28	2	42
Week 8	56	43	70

Week 12	84	71	98
Week 16	112	99	126
Week 20	140	127	154
Week 24	168	155	182
Week 28	196	183	210
Week 32	224	211	238
Week 36	252	239	266
Week 40	280	267	294
Week 44	308	295	322
Week 48	336	323	350
Week 52	364	351	EOT Date
Follow-up	EOT Date + 84	EOT Date +1	EOF Date

EOT=end of treatment; PRO=patient-reported outcomes; RB=rectal bleeding; SF=stool frequency
 *Endoscopy is performed only as part of the Week 52 assessments. To accommodate the scheduling of the endoscopy prior to the Week 52 visit, the start day of the analysis window will be extended to >342 for this parameter only if there is a valid assessment of SF and RB mapped to Week 52.
 *Follow-up visit applies to vital sign and weight assessments only.

Table 7: Visit Windows (Study Day Based) – ADA Assessments

Visit	Planned Study Day	Start Day of Window	End Day of Window
Week 12	84	2	126
Week 24	168	127	210
Week 36	252	211	EOT Date

ADA=anti-drug antibody; EOT=end of treatment
 *Following the implementation of Protocol Amendment 3, ADA assessments are not performed at Week 52.

Table 8: Visit Windows (Study Day Based) – [REDACTED] and ECG Assessments

Visit	Planned Study Day	Start Day of Window	End Day of Window
Week 12	84	2	126
Week 24	168	127	266
Week 52	364	267	EOT Date

ECG=electrocardiogram; EOT=end of treatment; [REDACTED]

Table 9: Visit Windows (Study Day Based) – Safety Lab, Physical Examination, and Neurological Testing Assessments

Visit	Planned Study Day	Start Day of Window	End Day of Window
Week 12	84	2	126
Week 24	168	127	210
Week 36	252	211	308
Week 52	364	309	EOT Date
Follow-up	EOT Date + 84	EOT Date + 1	EOF Date
EOF=end of follow-up; EOT=end of treatment			

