### **6.2.3 Dosing**

Investigational product (ontamalimab or placebo) will be administered subcutaneously by qualified site personnel Q4W up to Week 52. See Section 7.3 for the timing of dosing relative to other procedures.

Investigational product should be administered in the anterolateral right or left thigh. If there are clinical reasons why the investigational product cannot be administered in the thigh, the investigational product may be administered in the deltoid area or abdomen with appropriate documentation. The location of the investigational product administration will be recorded.

After the first administration of investigational product, the subject must be observed by a member of the study staff for at least 30 minutes (the total duration should be determined at the discretion of the investigator). For subsequent administrations, observation of the subject is at the discretion of the investigator. Injection site and allergic reaction monitoring should be completed by a member of the study staff.

Principal investigators are responsible for ensuring that all study and nonstudy personnel identified to administer investigational product are qualified, with documented training and delegation of responsibilities prior to their first investigational product administration visit at subjects' homes (see Section 10.2.1).

In a situation in which a subject is not able to visit the study site due to a pandemic (eg, coronavirus disease [COVID-19]) or other future similar unexpected public health concerns requiring physical distancing that may result in subjects missing their visits, DTP investigational product administration options may be available, in accordance with local regulations (refer to DTP guidance document).

All subjects and nonstudy personnel performing the investigational product administration must receive training in order to receive DTP shipments. Training will include how to identify hypersensitivity reactions, inject the IP, and properly dispose of IP after use. Training may be in person or via telephone call. All DTP shipments will require pre-administration and post-administration calls by the site staff to assess and monitor subject's health status and safety; to review any AEs, concomitant medications, and diary assessments; and to perform the neurological questionnaire assessment by the investigator. These calls must be appropriately recorded in the source document.

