It is important to note that assessments based on neurological evaluations are collected and evaluated in a different manner than observed or volunteered AEs. Given these differences, no attempt will be made to reconcile any apparent discrepancies between observed or volunteered AEs and data from neurological assessment collected from subjects. Investigators may determine if any finding on neurological testing constitutes an AE. Adverse event incidence rates will not be calculated from these neurological evaluation data but rather from the AE information recorded by the investigator.

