12.5 Repeated or Unscheduled Assessments of Safety Parameters

Assessments will be assigned to visits based on the date the assessment took place regardless of the completed CRF page. Assessments will be mapped to visits as outlined in [Table 6](#) to Table 9.

If a subject has more than 1 assessment mapped into a given study visit with non-missing results, the assessment closest to the planned visit will be used for analysis. However, all post-MNT baseline assessments will be used for PCI value determination.

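### An abnormal early-termination or unscheduled neurological examination can be left out of the by-visit domain table in SAP 7.6.1, because the exemption in SAP 12.5 covers PCI values only

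*SAP*

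**What the plan says.** SAP 12.3 assigns assessments to visits by date, whatever CRF page they were entered on. Where more than one non-missing result falls in a window, the rule is that "the assessment closest to the planned visit will be used for analysis"; if two are equally close, the later one is taken. SAP Table 9, which covers "Safety Lab, Physical Examination, and Neurological Testing Assessments", sets the windows: Week 12 is Days 2 to 126, Week 24 is Days 127 to 210, Week 36 is Days 211 to 308, and Week 52 runs from Day 309 to the end-of-treatment (EOT) date, followed by a follow-up window.

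SAP 12.5 repeats the rule for repeated or unscheduled safety assessments and adds one exemption: "However, all post-MNT baseline assessments will be used for PCI value determination". PCI criteria appear in SAP Tables 3 to 5, for laboratory tests, vital signs and ECG. None is defined for neurological results.

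SAP 7.6.1 says that each neurological domain "will be summarized by the result category (abnormal, normal, not done) at each visit and by treatment group". Results with unexplained abnormal findings are also summarized by visit. Referrals for neurological consultation and their outcomes (including PML or no PML) are summarized by treatment group, with no by-visit restriction. Evaluation and consultation results are listed for the Safety Set.

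**The concern.** PML is the one important potential risk named in SAP 7.1.1, and Protocol 7.3.3.3 gives monitoring for its signs as the purpose of the targeted neurological assessment. For such a measure, the natural safety question is whether a subject ever had an abnormal examination on treatment. The plan has no any-time or worst-result neurological summary. It has by-visit tables that admit one examination per window.

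That matters more in this trial than in one that runs to plan. Under Amendment 3 each subject's next visit becomes the Week 52/ET visit (Protocol 7.2.2.1), and the Week 52 assessments serve as the ET assessments (Protocol 7.2.2.2). Because mapping is by date, an ET examination soon after a quarterly one shares its window and competes with it. The examination lost would then be the subject's last on treatment. Unscheduled visits (Protocol 7.2) are a second source of competing results.

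Adverse event tables are not a sure substitute. Protocol 7.3.3.3 lets the investigator decide whether a finding is an AE, and says that "no attempt will be made to reconcile any apparent discrepancies between observed or volunteered AEs and data from neurological assessment" will be reconciled.

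**Working it through.** The plan states no figure to reproduce. The check applies the written rule to dates.

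**Inputs.** Windows and planned days (84, 168, 252, 364): SAP Table 9; the Week 24 row, for instance, reads "Week 24 168 127 210" (planned day, start, end). Selection rule: SAP 12.3. Quarterly frequency: Protocol Table 4. ET timing: no later than 4 weeks (±10 days) after the last visit, Protocol 7.2.2.1.

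**Rule.** For each examination in a window, distance = |study day − planned day|. The smallest distance is kept; ties go to the later date.

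**Step 1: quarterly examination on its planned day.** Its distance is 0, so any other examination in that window is dropped. Take ET between 28 − 10 = 18 and 28 + 10 = 38 days later, which gives 21 possible days:

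- after Day 84: Days 102 to 122, all inside the window ending Day 126;
- after Day 168: Days 186 to 206, all inside the window ending Day 210;
- after Day 252: Days 270 to 290, all inside the window ending Day 308.

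In each case ET shares the window on 21 of 21 days and is never the closest. For a normal result on Day 168 and an abnormal one on Day 196, the distances are 0 and 28, so Week 24 is tabulated as normal.

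**Step 2: every possible last visit, on schedule, with ET exactly 28 days later.**

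| Last visit | ET day | Window of ET | Quarterly examination in same window | ET examination |
|---|---|---|---|---|
| Week 4 | 56 | Week 12 | none | kept |
| Week 8 | 84 | Week 12 | none | kept |
| Week 12 | 112 | Week 12 | Day 84 | dropped |
| Week 16 | 140 | Week 24 | none | kept |
| Week 20 | 168 | Week 24 | none | kept |
| Week 24 | 196 | Week 24 | Day 168 | dropped |
| Week 28 | 224 | Week 36 | none | kept |
| Week 32 | 252 | Week 36 | none | kept |
| Week 36 | 280 | Week 36 | Day 252 | dropped |
| Week 40 | 308 | Week 36 | Day 252 | dropped |
| Week 44 | 336 | Week 52 | none | kept |
| Week 48 | 364 | Week 52 | none | kept |

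The ET examination is dropped in 4 of 12 positions. The Week 40 case sits on the window edge: over 18 to 38 days after Day 280 (Days 298 to 318), ET is dropped on Days 298 to 308 (11 days) and kept on Days 309 to 318 (10 days).

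**Step 3: quarterly examination off schedule.** If it was 10 days early, on Day 158 (distance 10), an ET examination 28 days later on Day 186 has distance 18 and is still dropped. ET only 18 to 20 days later (Days 176 to 178, distances 8, 9 and 10) would be kept, the last by the tie rule. The loss is therefore usual in this situation, not invariable.

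**The case against.** A by-visit table needs one record per visit, so the rule itself is ordinary, and the other neurological outputs cover much of the ground. A reader might infer that a PML case could be hidden. The documents do not support that. The referral and consultation summary is not by visit, so windowing does not touch it. Protocol 7.3.3.3 requires urgent referral to a neurologist for unexplained abnormal findings and immediate notice to the sponsor, with prompt review of suspected PML by monitoring committee members. Investigators may record a finding as an AE, important potential risks are listed under SAP 7.1.1, and the listings keep all neurological results. All of this stands. It leaves abnormalities that were explained or transient, which reach no summary other than the by-visit tables unless recorded as AEs.

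A reader might also infer that subjects dosed at home lose most of their neurological data, because Protocol 6.2.3 requires calls with each direct-to-patient shipment "to perform the neurological questionnaire assessment by the investigator". That is not established either. The calls must be recorded in source documents; nothing says that the questionnaire is entered in the clinical database or counts as the targeted examination tabulated in SAP 7.6.1.

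SAP 7 defines a final on-treatment assessment, which would capture the ET examination if it were tabulated. It is not assigned to any neurological table, and it would not capture unscheduled examinations. Finally, table specifications are in a separate document (SAP 1), so an any-time row there cannot be excluded.

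**Conclusion.** The point holds in a narrow form. Under the written rule, an abnormal ET or unscheduled examination can be omitted from the by-visit neurological summaries when the closest examination in the window is normal. If the closest one is also abnormal, the window is still counted as abnormal. In the on-schedule case, the ET examination is dropped after a last visit at Week 12, 24, 36 or 40. The documents give no abnormality rate and no distribution of last visits, so the number of subjects affected cannot be estimated.

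This is a minor reporting gap, not a failure of PML surveillance. It rests on three assumptions: the quarterly examinations took place on or near their planned days; the EOT date is not before the ET examination (otherwise that examination would map to follow-up); and the targeted examination is part of the ET visit. The last is inferred from the Week 52 row of SAP Table 9, because the neurological row of the schedule is not in the text available for this review.

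**What to change.** Keep the by-visit table as it is. In SAP 7.6.1 add, for each domain and treatment group, the number and percentage of subjects with any abnormal and with any unexplained abnormal examination after maintenance baseline, using all scheduled, ET and unscheduled assessments. In SAP 12.5, extend the sentence that exempts PCI values so that it also covers these neurological summaries. Include remote questionnaire results only if they are in the clinical database, and mark them as remote.

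The cost is one sentence and one block of rows, from examinations already collected. The drawback is that the new counts may include transient findings, so they should be read beside the referral summary. No examination, referral or treatment rule changes.
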